#### 4.7 Discontinuation of treatment within the assigned treatment arm 4.7.1 Discontinuation for toxicity

As applicable, when toxicity cannot be managed through modification of treatment regimen, assigned treatment may be discontinued and participant managed according to best medical judgment.

# 4.7.2 Discontinuation for pregnancy

If a participant becomes pregnant, methotrexate and mycophenolate must be discontinued as methotrexate is known to increase the risk of spontaneous abortion and malformations and mycophenolate is known to increase the risk of malformations. Consideration should be given to discontinuation of azathioprine, cyclosporine, tacrolimus, and adalimumab. Participants should be managed according to best medical judgment.

# 4.8 Ancillary therapy

# 4.8.1 Regional corticosteroid Injections

The MUST Trial demonstrated that the majority of patients with uveitic macular edema require supplemental regional corticosteroid injections (either periocular or intravitreal) to improve the macular edema, but that they typically need only one or two injections. Therefore, participants in the ADVISE Trial with uveitic macular edema will be permitted a regional corticosteroid injection within the first 2 months, if needed, and a second injection during months 6 to 8 (if needed) for persistent macular edema (to meet patients' clinical needs without contaminating key outcomes). Acceptable regional injections are: 1) periocular triamcinolone acetonide 40 mg, 2) intravitreal triamcinolone acetonide 4 mg (Triesence® [Alcon Laboratories, Inc., Fort Worth, TX] preferred if available due to its being preservative free for intravitreal use).or 3) the dexamethasone intravitreal pellet (Ozurdex ®, Allergan, Inc., Irvine, CA). If a participant is given an injection during the first 2 months of the trial, the dose of prednisone should not go below 7.5 mg/day (or if already <7.5 mg/day, should not be tapered further) until 3 months after the injection, as the primary outcome only can be ascertained 3 months after an injection. Allowing the limited use of regional corticosteroid injections for uveitic macular edema is necessary for proper clinical care, and the restrictions on their use will permit evaluation of the trial's outcomes.

# 4.8.2 Topical corticosteroids

- Adjunctive use of high doses of topical corticosteroids (up to one drop hourly of prednisolone acetate 1%, prednisolone sodium phosphate 1% or loteprednol etabonate 0.5%, or one drop six times daily of difluprednate 0.05%) is permitted for up to two weeks after anterior chamber uveitic activity is first observed.
- Upon quiescence of the anterior chamber inflammation, topical corticosteroids should be tapered
- Maintenance therapy of not more than prednisolone acetate 1% or loteprednol 0.5% three times daily or difluprednate 0.05% one drop daily is permitted.
- Failure to control anterior chamber inflammation using this approach should be addressed with systemic corticosteroids and immunosuppression.
- Discontinuation of such therapy, when feasible, is encouraged

# 4.8.3 Non-corticosteroid ophthalmic medications

These may be used according to best medical judgment.

# 4.8.4 Systemic medications other than corticosteroids and immunosuppressive drugs

These may be used according to best medical judgment.

# 4.8.5 Treatment monitoring

Treatment will be monitored for consistency with the treatment guideline by a member of the MTQAC, MTQAC will monitor treatment patterns as revealed in the data stream, site visits, etc., and investigate inconsistencies with treatment guidelines, providing remediation as appropriate.

#### 5. Study treatment procurement

Adalimumab will be donated by AbbVie (Chicago, IL); distribution to clinical centers is described in the manual of procedures. Prednisone and conventional immunosuppressive study treatments are not provided by the study and will be obtained per standard care.

#### 6. Possible side effects and complications of study treatments

Although there are potential risks associated with systemic corticosteroids and immunosuppression, they typically are reversible with dose reduction or discontinuation of the drug. The MUST Trial and Follow-up Study demonstrated that there was essentially no increased risk of these events compared to treatment with a strictly regional therapy, the fluocinolone acetonide implant, with the one exception of a greater use of antibiotics among participants receiving systemic therapy. Hence, with appropriate use, these risks can be minimized. Thus, the risks associated with participation in the ADVISE Trial are expected not to be greater than those associated with clinical care for patients with these uveitides. Possible side effects of the randomly assigned study treatments and of corticosteroids are summarized in Table 7.

Patients in ADVISE Trial will receive oral corticosteroids for treatment of uveitis, as they would in clinical care. The potential side effects of oral corticosteroids include water retention, weight gain, headache, muscle weakness, loss of muscle mass, face puffiness, growth of facial hair, easy bruising, acne, rounding of the upper back, irregular menstrual periods, insomnia, mood swings, increased energy, personality change, hypertension, hyperglycemia, and hypercholesterolemia. Oral corticosteroid therapy may lower resistance to infections, make infections harder to treat, slow wound healing, and increase the risk of osteoporosis. Aseptic necrosis of bone is a rare but serious complication. For persons already at risk of congestive heart failure, corticosteroids can increase the risk. Side effects occur more often with longer treatment and with higher doses, and typically resolve when dosage is lowered or treatment is discontinued. As noted previously, serious complications such as these are very rare, particularly when appropriate management is used, as was done in the MUST Trial, including aggressive tapering of prednisone to a dose <7.5 mg/dav In the MUST Trial and Followup Study, there generally was no significant increase is systemic side effects with systemic therapy through 7 years of follow-up. Ocular side effects seen in the eyes of patients with uveitis treated with systemic corticosteroids include the need for cataract surgery at ~6%/year, ocular hypertension at 3%/year, and glaucoma at 1.3%/year. Typically, these side effects are lower than with alternatively local therapies, as was demonstrated in the MUST Trial.

In addition to corticosteroids, patients in the ADVISE Trial will receive immunosuppressive agents, either conventional (small molecule) drugs or the biologic adalimumab. For many of these diseases, immunosuppression has been shown to produce superior outcomes. The eligibility criteria select patients for whom immunosuppression is indicated, so that patients are not expected to experience any greater risk than would be seen with clinical care. Conventional immunosuppressive agents with activity against uveitis that will be used in ADVISE are the antimetabolites, azathioprine (AZA), methotrexate (MTX), and mycophenolate mofetil (MMF); and the calcineurin (or T cell) inhibitors, cyclosporine (CSA) and tacrolimus (TAC). Because of the potential increased risk of cancer associated with alkylating agent use. and because they are not used in conjunction with other immunosuppressive drugs, cyclophosphamide and chlorambucil will not be used in the trial, unless the patient suffers sufficient relapses that (s)he is treated with best medical judgment. Each of these agents is associated with its own spectrum of potential systemic side effects. Side effects associated with these medications that are medically important and expected to occur with detectable frequency during the trial are described below. The ADVISE Trial will conduct surveillance for these potential risks in a protocol-directed manner that approximates medical care (see Table 7). However, the side effects mentioned below did not occur with higher frequency in the systemic therapy group of the MUST Trial than in the strictly local therapy implant group.15,22,24

Bone marrow suppression: a) Reversible neutropenia – which may occur with AZA, MTX, MMF, TAC – will be evaluated over time as the cumulative proportion having a total white blood cell (WBC) count 2500 cells/µL or fewer, which still is above the level for an increased risk of infection, and is a common indication for interruption of therapy. Change in WBC count from baseline and use of granulocyte stimulatory factors also will be noted; b) Reversible thrombocytopenia – which may occur with AZA, MTX, MMF, TAC – will be evaluated over time as the cumulative proportion having a platelet count 100,000/µL or fewer, which is a common indication for suspension of therapy. Hemorrhagic events and requirement for platelet transfusion or other treatments for thrombocytopenia also will be noted; c) Reversible anemia – which may occur with AZA, MTX, MMF, CSA, TAC – will be evaluated over time as the cumulative proportion having a hemoglobin level ≤10 g/dL, a level often considered clinically meaningful. Use of transfusions and of erythropoietin also will be noted; and the occurrence of myelodysplasia will be noted if confirmed in medical records.

*Reversible hepatotoxicity* -- which may occur with AZA, MTX, MMF, CSA, and TAC -- will be evaluated over time as the cumulative proportion with any of the following, verified in medical records: aspartate aminotransferase (AST) or alanine aminotransferase (ALT) levels greater than two times the upper range of normal confirmed by repeat testing; OR discontinuation of an immunosuppressive agent due to hepatotoxicity. Cases of persistent elevation of AST and/or ALT after discontinuation of the offending agent will be noted.

*Reversible nephrotoxicity* -- which may occur with CSA and TAC -- will be evaluated over time as the cumulative proportion with: serum creatinine level elevated 30% above baseline or to a level of 1.5 mg/dL or higher OR discontinuation of an immunosuppressive drug for renal toxicity. Persistent renal insufficiency will be noted.

*Pregnancy risks*: MTX and MMF are associated with increased risk of first trimester pregnancy loss and congenital malformations; women of child bearing potential and men taking MTX are advised to use adequate birth control during the trial, and especially if taking these medications.

*Infection:* even without an increased risk of leukopenia among patients in the (unmasked) MUST Trial on systemic therapy, there was an increased use of antibiotics for infection. However, there were no long-term sequelae from these infections, and no increase in the risk of hospitalization for infection. Patients will be queried about infections at every visit, and medical records reviewed as necessary, to monitor for infections. Hospitalization data also will be collected. In non-uveitis use (e.g., transplants) some immunosuppressive regimens may increase the risk of severe opportunistic infections (e.g., progressive multifocal leukoencephalopathy), which can have serious consequences, including death. Although there were no such events in the MUST Trial, because of their rare nature, their possible occurrence in the ADVISE Trial or routine clinical practice using these drugs cannot be excluded.

Additional recognized potential complications of potent immunosuppressive therapy will be deemed to be present when diagnosis is confirmed by medical records. These conditions specifically will include a diagnosis of any of the following conditions (if not present at baseline): a) liver cirrhosis; b) interstitial pneumonitis; c) possibly malignancy (drug-specific); d) end-stage renal insufficiency.

In addition to these small molecule immunosuppressive agents, the anti-TNF-α biologic agent adalimumab will be used. The most common adverse reaction of adalimumab is redness, itching, pain, or swelling at the injection site, reported in 20% of patients. Other less common adverse events include: increased risk of infections, particularly tuberculosis, fungal infections, and herpes zoster. Patents randomized to adalimumab will be instructed not to get any live

vaccines. Other uncommon potential adverse effects include gastrointestinal symptoms such as nausea, vomiting, abdominal pain, or diarrhea; reversible bone marrow suppression; and reversible hepatotoxicity. Other rare adverse events include: development of anti-adalimumab antibodies and a lupus erythematosus-like syndrome, and a worsening of demyelinating disease, such as multiple sclerosis. All patients enrolled in the ADVISE Trial will have tuberculosis testing with either an interferon-γ release assay test, such as the Quantiferon-gold test and testing for active hepatitis B or C infection prior to enrollment. Active tuberculosis and untreated latent tuberculosis and untreated active hepatitis B or C infection are exclusions to participation. Because of the increased risk of multiple sclerosis in patients with pars planitis and undifferentiated intermediate uveitis, all potential participants with these two diseases will undergo neuro-imaging with a gadolinium enhanced MRI scan and patients with evidence of possible demyelination are excluded from the trial.

Use of the following medications are prohibited during the trial for safety reasons

- Live vaccines
- Substrates for the multidrug efflux transporter P-glycoprotein or the organic anion transporter proteins (OATP) and for which elevated plasma concentrations are associated with serious and/or life threatening events, e.g. bosentan, dabigatran etexilate and aliskiren.
- Products containing Hypericum perforatum (St John's Wort) to avoid risk of interaction with tacrolimus that lead to either a decrease in blood concentrations of tacrolimus and reduced clinical effect of tacrolimus, or an increase in blood concentrations of tacrolimus and risk of tacrolimus

Treatment	Group affected	Systemic	Monitoring & Prevention Strategy
Corticosteroids	Both groups	Hyperglycemia	History; CMP testing
		Hypertension	History; BP measurement
		Osteoporosis	Routine monitoring/ data collection
		Hyperlipidemia	Routine monitoring/ data collection
		Infection	Routine monitoring/ data collection
		Cardiovascular Disease	Routine monitoring/ data collection; Monitor risk factors (per above)
		Cataract	Slit lamp examination/Eye Exam
		Intraocular Pressure Elevation and Glaucoma	Eye Examination
Adalimumab	Adalimumab	Infection	Pre-randomization tuberculosis and hepatitis B and C testing; Routine monitoring/ data collection. Live vaccines should not be given.
		Worsening of multiple sclerosis	MRI of patients with intermediate uveitis at BL; Routine monitoring/ data collection
		Injection Site Reaction*	Routine monitoring/ data collection
		Bone marrow toxicity*	CBC testing
		Hepatotoxicity*	CMP testing, pre-treatment Hepatitis panel
Methotrexate	Conventional	Bone marrow toxicity*	CBC testing
		Hepatotoxicity*	CMP testing, pre-treatment Hepatitis panel
		GI intolerance*	History/Routine monitoring
		Teratogenicity/ Miscarriage	Birth control use for women and men
		Alopecia*	Routine monitoring/ data collection
Mycophenolate	Conventional	Bone marrow toxicity*	CBC testing
		Hepatotoxicity*	CMP testing, pre-treatment Hepatitis panel
		GI intolerance*	History/Routine monitoring
		Teratogenicity	Birth control use
		Possibly PML (disputed)	History/Routine monitoring

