# 3.1 Design elements

- Randomized, parallel-treatment, controlled comparative effectiveness clinical trial
- Randomization stratified by:
  - Whether patient is receiving zero or one immunosuppressive agent at enrollment
  - Whether the initial dose of prednisone in the trial will be <30 mg/day or ≥ 30 mg/day

- The unit of randomization is the patient
- The unit of analysis for the primary outcome is the patient
- Allocation ratio 1:1
- Multicenter, international
- Fixed sample size = 222 (111 per treatment group)
- Unmasked treatment administration and outcome assessments (participants, study ophthalmologists, visual function examiners, and study coordinators are all unmasked).
- Masked assessment of photographic images and OCT by the RC (graders masked)
  - All patients
    - OCT at baseline, 3, 6, and 12 months
    - Retinal color photographs at baseline, 6 and 12 months
- Disease-specific image or OCT, as applicable, at baseline, 1, 3, 6, and 12 monthsAnniversary close-out at the 12-month visit
- First patient enrolled in September 2019; the end of the trial (completion of follow-up of last patient enrolled) is expected to be February 2023.
- Conducted under IND 132532

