# Management of conventional immunosuppressive agents for patients who are on one at baseline

Patients in the adalimumab treatment group who already are taking a conventional immunosuppressive drug will continue that drug throughout the study (in addition to the adalimumab) unless some contraindication to continuation arises. Those for whom existing immunosuppressive therapy is deemed non-useful should discontinue it before entering the study.

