# 4.5 Management of uveitis reactivation

The guidelines for managing uveitis reactivation are summarized in tables 6a. *Reactivation management guidelines: Prednisone* and 6b. *Reactivation management guidelines: Immunosuppression*.

The prednisone dose to be used for uveitis reactivation will depend upon whether the reactivation occurs during the prednisone taper or after prednisone cessation. If the uveitis reactivates during the prednisone taper, the dose of prednisone will be at least doubled, up to the maximum allowed dose (1mg/kg/day up to 60 mg/day), depending on the severity of the reactivation per table 6a. If uveitis reactivates after achieving prednisone cessation, prednisone will be reinstated at a dose of at least 10 mg/day up to the maximum allowed dose (i.e., 1 mg/kg/day if < 60 kg or 60 mg/day if  $\geq$  60 kg), depending on the severity of the reactivation. The study physician will determine whether to advance immunosuppression per best medical judgment.

As adalimumab is FDA-approved at only a single dose, advancement of immunosuppressive therapy will focus on the addition or increase in dose of conventional immunosuppressive agents for both treatment arms. The advancement of conventional immunosuppressive agents will depend upon number and dose(s) of the current medications being used.

For patients on less than the maximum dose of a conventional immunosuppressive agent, it should be increased to the maximum dose in Table 5, as applicable and tolerated. For patients on the maximum dose of a single immunosuppressive drug, a second agent from the other class should be added. For patients on an antimetabolite, a calcineurin inhibitor will be added and vice versa. For patients already on 2 immunosuppressive drugs at maximum doses, best medical judgment will be used, including changing one or both of the currently used immunosuppressive agents.

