#### 4.6 Monitoring for toxicity of immunosuppressive drugs

Patients will be monitored for potential toxicities of adalimumab or conventional immunosuppressive therapy/therapies using the schedule described in the Trial's follow-up schedule (Table 2), i.e., complete blood count and chemistry panel including creatinine and liver enzymes will be conducted at every study visit and monitoring and prevention strategies will be implemented as detailed in Table 7. Potential Risks of Therapy. As applicable, additional monitoring studies should be carried out per routine care. When potential toxicities are encountered, modification of therapy, including dose reduction or discontinuation as clinically appropriate, should be done along the lines indicated in published guidelines.

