# Table 8. Potential risks of therapy

Treatment	Group affected	Systemic	Monitoring & Prevention Strategy
Azathioprine	Conventional	Bone marrow toxicity*	CBC testing
		Hepatotoxicity*	CMP testing, pre-treatment Hepatitis panel
		GI intolerance*	History/Routine monitoring
Cyclosporine	Conventional	Hypertension*	History; BP measurement
		Renal insufficiency*	CMP testing
		Tremor/paresthesia*	History/Routine monitoring
		Hirsutism*	History/Routine monitoring
		Gingival hyperplasia*	History/Routine monitoring
Tacrolimus	Conventional	Hypertension*	History; BP measurement
		Renal insufficiency*	CMP testing
		Tremor/paresthesia*	History/Routine monitoring
		Hyperglycemia*	History; CMP testing
		Interactions with products containing Hypericum perforatum	Products containing Hypericum perforatum (St John´s Wort).may not used during the study

\*Usually reversible with dose adjustment or cessation of therapy

CMP=complete metabolic panel; BP=blood pressure; CBC=complete blood count

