# 8. Sample size and statistical methods

# 8.1 Hypotheses

The primary hypothesis is that adalimumab will be superior to conventional immunosuppression for corticosteroid sparing, as determined by the proportion of participants that achieve the primary outcome, namely inactive uveitis and prednisone  $\leq$ 7.5 mg/day for 2 visits  $\geq$ 28 days apart by 6 months of follow-up. The 6-month time frame was chosen to allow sufficient time to observe the primary outcome regardless of the patient's prednisone dose at randomization and is likely to be more robust to imbalances.

Secondary hypothesis are that adalimumab will be superior to conventional immunosuppression for:

- Corticosteroid sparing (inactive uveitis and prednisone <7.5 mg/day for 2 visits >28 days) apart by one year of follow-up
- Prednisone discontinuation (inactive uveitis for 2 visits >28 days after discontinuation of prednisone) by one year.

Furthermore, we hypothesize that these benefits will be accomplished with no increase in ocular or systemic adverse events (other than injection site reactions) with adalimumab, and that both approaches will produce similarly visual acuity and incidences of uveitic complications.

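### The protocol's hepatotoxicity event misses liver-enzyme elevations that fall after a dose reduction before any repeat test, or that first appear at month 12 without a retest, so its count depends partly on unmasked clinicians' choices

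*Protocol*

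**What the plan says.** Protocol section 6 evaluates hepatotoxicity as a cumulative proportion, verified in medical records. A patient has the event if AST or ALT is "greater than two times the upper range of normal confirmed by repeat testing; OR discontinuation of an immunosuppressive agent due to hepatotoxicity".

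Liver enzymes are measured at every study visit (protocol sections 3.7 and 4.6): monthly to month 6, then at months 8, 10 and 12. Beyond that, section 4.6 says that, as applicable, "additional monitoring studies should be carried out per routine care". Neither document requires a confirmatory retest or gives a window for one.

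When toxicity is suspected, section 4.6 calls for "modification of therapy, including dose reduction or discontinuation as clinically appropriate", along the lines of published guidelines. Section 4.7.1 allows the assigned treatment to be stopped when modifying the regimen does not manage the toxicity. The footnote to the table of potential risks of therapy marks hepatotoxicity as "Usually reversible with dose adjustment or cessation of therapy".

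The SAP (section 4.2) gives elevated liver enzymes as an example of a systemic adverse event, without a threshold or confirmation rule. It does not say whether the section 6 definition applies.

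**The concern.** The definition has two limbs, confirmation and discontinuation, but the response the protocol expects first is a third one, dose modification. A patient managed that way, successfully, can leave the count.

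This matters because protocol section 8.1 hypothesizes "no increase in ocular or systemic adverse events (other than injection site reactions) with adalimumab", and hepatotoxicity is a listed risk in both arms. Section 3.1 states that "participants, study ophthalmologists, visual function examiners, and study coordinators are all unmasked", so the people who decide whether to retest, reduce or stop know the assignment. Their options also differ. Section 4.5 begins its reasoning on dose advancement with "As adalimumab is FDA-approved at only a single dose", whereas Table 5 gives the antimetabolites and tacrolimus a starting dose and a higher maximum. If elevations in one arm more often lead to a dose cut and those in the other to a stop, equal biology could give unequal counts.

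**Working it through.** The plan gives no expected rate for this event, so there is no figure to reproduce. The check has two parts.

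**1. Which elevations count**

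The gaps from each follow-up panel to the next scheduled one are 1, 1, 1, 1, 1, 2, 2 and 2 months for V02 to V09. V10 is the close-out visit and has none.

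| Course after a first value above 2 x ULN | Meets the section 6 event? |
|---|---|
| Still above 2 x ULN at the next study panel | Yes, confirmed |
| Prompt routine-care retest also above 2 x ULN | Yes, confirmed |
| Agent stopped or switched for hepatotoxicity | Yes, discontinued |
| Dose reduced, value at or below 2 x ULN at the first repeat | No |
| First seen at V10, no routine-care retest, no stop | No |
| Temporary interruption, then recovery | Not stated |

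The white cell, platelet, hemoglobin and creatinine definitions in the same section need no repeat test. Hepatotoxicity is the only laboratory event there that does.

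**2. How much it could matter**

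Inputs: n = 111 per arm (protocol 3.1). Two quantities are assumed because the documents give neither: p, the risk of a first AST or ALT above 2 x ULN, and u, the share of those not counted.

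*A plausible range for u.* Suppose 1/9 (equal per visit) to 2/12 (uniform onset over 12 months) of first elevations appear at V10 and none of these is retested. Suppose also that 0 to 50% of the rest normalize before a repeat. Counted proportion = p x (1 - share at V10) x (1 - share normalized). At p = 10%:

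- highest: 10% x 8/9 x 1 = 8.9%, so u = 0.11
- lowest: 10% x 10/12 x 0.5 = 4.2%, so u = 0.58

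*Equal u in both arms.* The risk ratio is unbiased and only precision is lost. Counted events per arm c = 111 x p x (1 - u); 95% limits around a true ratio of 1 are exp(±1.96 x sqrt(2 x (1/c - 1/111))). At p = 10%:

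| u | c | 95% limits |
|---|---|---|
| 0 | 11.10 | 0.45 to 2.20 |
| 0.25 | 8.33 | 0.40 to 2.52 |
| 0.50 | 5.55 | 0.32 to 3.15 |

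*Unequal u, 0.25 against 0.50, no true difference.* Counted proportions are 0.75p and 0.5p. The false risk ratio is 0.75/0.5 = 1.50, or 0.67 if the arms are reversed. The false difference is 0.25p. The 95% half-width is 1.96 x sqrt((0.75p(1 - 0.75p) + 0.5p(1 - 0.5p))/111).

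| p | False difference (points) | 95% half-width (points) |
|---|---|---|
| 5% | 1.25 | 4.6 |
| 10% | 2.5 | 6.4 |
| 20% | 5.0 | 8.7 |

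In each case the distortion is smaller than sampling error.

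**The case against.** Confirmation is a legitimate filter. Patients may enter with AST or ALT up to 1.5 x ULN (section 3.5), so a rise of 2.0/1.5 - 1 = 33% crosses the threshold, and a single value that has dropped by the next test is what such a filter is meant to remove. The every-visit panels act as a repeat within one or two months at eight of nine follow-up visits. The month-12 case is ordinary truncation at the end of follow-up, on the same schedule in both arms. All of this stands and is why the confirmed event should stay. It does not fully answer the dose-reduction case, where a fall after the dose is cut may reflect a real drug effect.

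The retest rule may exist elsewhere. Section 4.6 defers to published guidelines, and the protocol places treatment detail in the Manual of Procedures. Neither is available here, so this stands as a limit on the point.

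Two stronger readings are tempting. A reader might infer that these elevations vanish from the trial's safety record. The documents do not support that: adverse events go to the coordinating center, the monitoring committee receives safety summaries and between-arm comparisons (SAP 7.3), and the SAP's undefined liver-enzyme outcome may itself include unconfirmed values.

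A reader might also infer that the definition favors one arm. That is not supported either. A patient in the adalimumab arm already on a conventional drug "will continue that drug throughout the study (in addition to the adalimumab) unless some contraindication to continuation arises", and section 4.4 allows one to be added, so adjustable doses occur in both arms. The direction is unknown.

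**Conclusion.** The point holds in a narrow form. The section 6 event does not capture elevations that resolve after a dose reduction before any repeat, or those first seen at V10 without a routine-care retest. Its count therefore rests partly on unmasked decisions, with dose options that differ by arm.

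The size is modest. Under the assumed values (p of 5 to 20%, u of 0.25 against 0.50), the false difference is 1.25 to 5.0 points, each below its half-width of 4.6 to 8.7 points. These values are illustrations, not estimates. Only this derived safety event is affected; the primary outcome, power and safety monitoring are not. The point would shrink further if the Manual of Procedures or the cited guidelines require a retest. It is worth considering because the remedy is nearly free.

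**What to change.** Keep the confirmed-or-discontinued event in protocol section 6. In SAP section 4.2, define the liver-enzyme outcome along these lines: the cumulative proportion of participants with any AST or ALT above 2 x ULN on the scheduled panels V02 to V10 will be compared by arm, and the section 6 hepatotoxicity event will be reported beside it. Using scheduled panels only makes planned ascertainment the same in both arms and removes the dependence on who was retested or dose-reduced.

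The cost is one or two sentences. The panels are already taken at every visit, so there are no new visits or tests. The downside is that some transient elevations will be counted, which is the reason to keep the confirmed event alongside. No retest after V10 is needed; guaranteeing one would require a blood draw after close-out.

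An optional clarification is to state whether a temporary interruption counts as discontinuation.
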